Study Protocol with Statistical Analysis Plan

Study Title: Persisting Effects of Psilocybin

Clinical Trials ID (NCT number): NCT02971605

Last Protocol Approval Date: April 24, 2017

This open-label, non-blinded study will involve 12 volunteers who will receive a high dose of psilocybin under supportive conditions. Assessments (questionnaires and emotional tasks) will be conducted during screening sessions, and 1 day before, 1 week after, and 1 month after the high-dose psilocybin session. Functional magnetic resonance imaging (fMRI) will also be conducted 1 day before, 1 week after, and 1 month after the psilocybin session.

Primary objectives:

1. Assess the effects of psilocybin on the neural circuitry of emotion processing as measured by functional magnetic resonance imaging (fMRI) at 1 week and 1 month timepoints after psilocybin administration

Secondary objectives:

1. Assess the effects of psilocybin on emotional processing at 1 week and 1 month timepoints after psilocybin administration, well after acute subjective effects of the drug have subsided
2. Assess the effects of psilocybin on personality at 1 week and 1 month timepoints after psilocybin administration

Inclusion/Exclusion Criteria

Overview of Screening Procedures: Participants will be screened via telephone to determine whether they meet major inclusion/exclusion criteria, and thus whether they are eligible for an in-person screening session. Participants who do not fail telephone screening will be invited to BPRU on the Johns Hopkins Bayview Campus for in-person screening.

Consent will be obtained at the BPRU at a scheduled meeting after participants have passed telephone screening. Participants will be allowed to take as much time as necessary to decide whether or not to sign consent. Study staff will discuss the consent form with the participant after the participant has read the consent form. Study staff will ask questions to assess the individual's understanding of the consent form. Participants may take the consent form home to review and return to sign consent if they wish. Participants who might be eligible for a future study will be asked to complete IRB-approved HIPAA-IRB Form 3 "Authorization to contact you about future research studies". Participants' files will be kept in a locked room and treated as confidential research material. All data will be collected using the unique identification code numbers assigned to each participant upon entry to the study. No individual identifiable information will be released without written authorization. These procedures have been used in the past to protect confidentiality of study data and no instance of loss of confidential information has occurred.

Participants will be physically and psychologically healthy adult participants (approximately equal numbers of males and females) 18 to 45 years old. Non-English speakers and those with language or hearing impairments will not participate in the study. Participants will be recruited primarily from the Baltimore/Washington DC metro area. Participants will have used hallucinogens in the past, although preference will be given to those who have had minimal prior use (e.g. 1 to 2 prior uses) that was at least 3 months ago. Potential participants will be carefully screened to eliminate those with significant medical or psychiatric illnesses (see below for specific inclusion/exclusion criteria).

We expect to consent up to 100 volunteers at Johns Hopkins (some of whom will not pass the in-person screening), in order to achieve 12 participants who provide complete data.

Screening evaluation will include a history and physical examination, ECG, a 30 cc blood draw for medical screening (e.g., complete blood count and Quest Test 18T Comprehensive metabolic panel with eGFR), a personal and family medical history questionnaire, psychiatric interview (SCID-5), and a urine drug test.

As per standard BPRU screening procedures, screening physical examination and ECGs will be performed by BPRU medical staff (nurse, mid-level, or physician). ECGs will be interpreted by a cardiologist credentialed and privileged to read ECGs at Bayview Medical Center to determine if a significant abnormality exists. Participants will be requested to refrain from illicit drug use during the course of the study and a urine test will be conducted before the drug session (e.g., various opioids, stimulants and sedatives). Pregnant or nursing women are ineligible; female participants will receive a urine pregnancy test at intake and before the drug session, and must use effective methods of contraception during the study. With regard to psychiatric screening, clinical interviews and a structured psychiatric diagnostic interview (e.g., SCID) will be used to obtain baseline psychological data, including psychiatric history (including family history), psychoactive drug-use history, and information about employment status and current functioning (including mood and psychological and psychosomatic symptoms). Participants will be eligible if they are judged to be psychologically stable and do not meet any of the psychiatric exclusion criteria (as defined by DSM-V). Finally, participants will be required to meet standard inclusion/exclusion guidelines for brain imaging protocols (see below). All inclusion and exclusion criteria are described below:

Inclusion criteria:

- 18 to 45 years old
- Have given written informed consent
- Have at least a high-school level of education or equivalent (e.g. GED), and be fluent in English
- Be healthy and psychologically stable as determined by screening for medical and psychiatric problems via a personal interview, a medical questionnaire, a physical examination, an electrocardiogram (ECG), and routine medical blood and urinalysis laboratory tests
- Agree to consume approximately the same amount of caffeine-containing beverage (e.g., coffee, tea) that he/she consumes on a usual morning, before arriving at the research unit on the morning of the drug session day. If the participant does not routinely consume caffeinated beverages, he/she must agree not to do so on the session day.
- Agree to refrain from using any psychoactive drugs, including alcoholic beverages and nicotine, within 24 hours of each drug administration. The exception is caffeine.
- Agree not to take any PRN medications on the mornings of drug sessions
- Agree not to take sildenafil (Viagra®), tadalafil, or similar medications within 72 hours of each drug administration.
- Agree that for one week before each drug session, he/she will refrain from taking any nonprescription medication, nutritional supplement, or herbal supplement except when approved by the study investigators. Exceptions will be evaluated by the study investigators and will include acetaminophen, non-steroidal anti-inflammatory drugs, and common doses of vitamins and minerals.
- Have limited lifetime use of hallucinogens (at least one prior use of a hallucinogen, but preference will be given to those with the fewest number of prior exposures to a hallucinogen)
- Last hallucinogen use was at least 3 months ago (but preference will be given to those with a greater duration of time since last hallucinogen use)

General medical exclusion criteria:

- Women who are pregnant (as indicated by a positive urine pregnancy test assessed at intake and before each drug session) or nursing; women who are of child-bearing potential and sexually active who are not practicing an effective means of birth control.
- Cardiovascular conditions: coronary artery disease, stroke, angina, uncontrolled hypertension, a clinically significant ECG abnormality (e.g., atrial fibrillation), artificial heart valve, or TIA in the past year
- Epilepsy with history of seizures
- Insulin-dependent diabetes; if taking oral hypoglycemic agent, then no history of hypoglycemia

- Currently taking psychoactive prescription medication on a regular (e.g., daily) basis
- Currently taking on a regular (e.g., daily) basis any medications having a primary centrally-acting serotonergic effect, including MAOIs. For individuals who have intermittent or PRN use of such medications, psilocybin sessions will not be conducted until at least 5 half-lives of the agent have elapsed after the last dose.
- More than 20% outside the upper or lower range of ideal body weight according to Metropolitan Life height and weight table

Psychiatric Exclusion Criteria:

- Current or past history of meeting DSM-5 criteria for schizophrenia spectrum or other psychotic disorders (except substance/medication-induced or due to another medical condition), or Bipolar I or II Disorder
- Current or past history within the last 5 years of meeting DSM-5 criteria for a moderate or severe alcohol or drug use disorder (excluding caffeine and nicotine)
- Have a first or second-degree relative with schizophrenia spectrum or other psychotic disorders (except substance/medication-induced or due to another medical condition), or Bipolar I or II Disorder
- Has a psychiatric condition judged to be incompatible with establishment of rapport or safe exposure to psilocybin

Additional MRI Exclusion Criteria:

- Head trauma
- Claustrophobia incompatible with scanning
- Cardiac pacemaker
- Implanted cardiac defibrillator
- Aneurysm brain clip
- Inner ear implant
- Prior history as a metal worker and/or certain metallic objects in the body -- must complete MRI screening form (see eIRB Study Documents) and be approved by MRI technologist before each scan

Cardiovascular screening: There will be at least four blood pressure assessment occasions over at least two separate days. Within a day, assessment occasions will be separated by at least 15 minutes. Each assessment occasion will involve two or more blood pressure readings. To qualify for the study, the mean blood pressure (mm Hg) of the four or more assessment occasions will not exceed 140 systolic and 90 diastolic.

Blood pressure will be taken while subjects are at rest and have been seated or supine for at least 5 minutes. As recommended by the Joint National Committee on Prevention, Detection, Evaluation and Treatment of High Blood Pressure, these assessments will involve the average of 2 or more readings separated by two minutes. If the first 2 readings differ by more than 5 mm Hg, additional readings will be obtained and averaged. On one or more of the blood pressure measurement occasions, the volunteer will be acclimated to the automated blood pressure monitoring equipment by repeatedly taking blood pressure (at least 3 readings) with the device. Because it has been our experience that time-to-time blood pressure readings with the automated equipment can be variable due to measurement artifact, any reading that initially exceeds our threshold value will be reassessed twice within 4 minutes to assure accuracy.

Individuals who do not pass screening or choose not to participate will be asked whether they want us to keep their personal contact information. Identifiers for those individuals who do not want us to retain their information will be destroyed.

Drugs/ Substances/ Devices

Psilocybin dose: The dose of psilocybin administered in this study will be a moderately high dose (25 mg/70 kg). Psilocybin doses will be calculated based on body weight, which is consistent with our previous published studies (Griffiths et al. 2006, Griffiths et al. 2011, Johnson et al. 2014), controlled studies of psilocybin conducted in other research laboratories (Studerus et al. 2011), and our ongoing protocols. Evidence from our psilocybin dose-effects study (Griffiths et al., 2011) and a study of psilocybin compared to an active control drug (Griffiths et al., 2006) suggests that similar doses (20 mg/70 kg to 30 mg/70 kg) are associated with strong psychoactive effects, mystical-type effects, and enduring positive effects on mood and emotions that last for at least 14 months (Griffiths et al., 2008; Griffiths et al., 2011). The proposed 25 mg/70 kg dose is less than the maximum dose that has been administered in our laboratory, and it is in the range of doses examined extensively in previous studies with hallucinogen-naïve individuals (Malitz et al. 1960, Metzner, Litwin & Weil 1965, Pahnke 1969, Pahnke et al. 1969, Leuner 1962). The dose in the current study is considerably less than that (49 mg/70kg) administered safely under a previously authorized IND (Strassman 1992, 1998).

Study Statistics

Emotion processing tasks: Three well-established emotional processing tasks will be assessed in the fMRI scanner: an emotion recognition task, an emotional conflict Stroop task, and an emotional discrimination task. In the emotion recognition task (Gur et al. 2002, Moser et al. 2007, Gur et al. 2010), participants identify positive and negative emotional facial expressions, with identification of the gender of actors as a control task. The primary outcome measures of this task are accuracy, response time, and average BOLD response to positive and negative facial expressions during emotion identification compared to gender identification. In the emotional conflict Stroop task (Etkin et al. 2006, Egner et al. 2008), participants identify the valence of emotional facial expressions (targets) with overlaid emotional words (distractors). Targets and distractors may have congruent or incongruent emotional valence. Primary outcome measures are response time, accuracy, and average BOLD response to incongruent compared to congruent trials, separated by the emotional valence of the distractor. The emotional discrimination task consists of selecting between neutral and negative facial expressions (Hariri et al. 2002, Hariri et al. 2003, Kraehenmann et al. 2015), with selection of geometric figures as a control task. The primary outcome measure is BOLD response in the amygdala to facial affect discrimination compared to the control task (psilocybin was not shown to acutely affect accuracy and response time) (Kraehenmann et al. 2015). Participants will practice these tasks at each preparation meeting (Visits 3 and 4), before the baseline fMRI scan.

Resting-State Scans: Blood-oxygen dependent level (BOLD) data will be collected for 12 minutes during a period of rest. The participant will be asked to simply rest with eyes opened and focused on a single point in the participant's view. This scan will allow us to assess the long-term effects of psilocybin on resting-state brain function, and it will also allow us to assess static and dynamic functional connectivity between brain regions and compare results to numerous other fMRI studies of resting-state brain activity.

Longitudinal Emotion and Social Questionnaires: A battery of questionnaires will be completed one day before, one week after, and one month after psilocybin to assess emotional and social changes. This includes general [the Positive and Negative Affect Scale - X (Watson, Clark 1994) and the Profile of Mood States (McNair, Lorr & Droppleman 1992)] and emotion-specific [the Dispositional Positive Emotions Scale (Shiota, Keltner & John 2006), the Depression Anxiety Stress Scale (Lovibond, Lovibond 1995), and the State Trait Anxiety Inventory (Spielberger et al. 1983)] measures, as well as a measure of social cognition [the Social Value Orientation test (Murphy, Ackermann, & Handgraaf, 2011)]. Outcome measures will consist of the validated scale scores for each questionnaire.

Longitudinal and Follow-Up Questionnaires: Participants will complete the Big Five Inventory (BFI) (John, Naumann & Soto 2008) , the Brief Affective Neuroscience Personality Scales (BANPS) (Barrett, Robins & Janata 2013) , the Tellegen Absorption Scale (Tellegen, Atkinson 1974) , and the Emotion Regulation Questionnaire (Gross, John 2003) which are validated measures of personality traits. These questionnaires will be administered during screening and at the 1-month post-psilocybin imaging session, in order to test the hypothesis that openness and positive emotional personality traits will increase, and negative emotional personality traits will decrease, after psilocybin administration. A prior study in our laboratory found changes in the domain of openness following psilocybin (MacLean, Johnson & Griffiths 2011) .

Statistical plan

Assessing the effects of psilocybin on emotional processing. We hypothesize that psilocybin administration will lead to impaired recognition of negative emotional facial expressions, decreased emotional conflict to incongruent emotional stimuli during an emotional conflict processing task, decreased negative affect, and increased positive affect one week and one month after psilocybin administration, relative to baseline. Outcome measures of the emotion recognition task and emotional conflict Stroop task will be separately submitted to two-way repeated measures ANOVA, with assessment time-point (baseline, one week and one month post-psilocybin) and emotional valence of stimuli (positive vs negative) as within-subject factors. F-tests will be used to assess whether there is a main effect of assessment time point and an effect of the interaction between assessment time point and emotional valence on each outcome measure. Planned comparisons will be used to test the hypothesis of impaired responding to negative emotional stimuli (confirmed by finding increased reaction time and decreased accuracy), and facilitated responding to positive emotional stimuli (confirmed by finding decreased reaction time and increased accuracy) at each post-psilocybin time point (one week, one month) compared to baseline. Outcome measures of the longitudinal questionnaires will be separately submitted to a one-way repeated measures ANOVA, with assessment time-point as a within-subject factor. An F-test will be used to assess whether there is a main effect of assessment time point on each outcome measure.

Assessing the effects of psilocybin on the neural circuitry of emotion processing. We hypothesize that psilocybin administration will reduce amygdala BOLD response to negative emotional stimuli during emotion recognition and discrimination tasks, and ACC BOLD response during emotional conflict processing, one week and one month post-psilocybin. Whole-brain BOLD EPI data will undergo standard preprocessing (realignment/motion correction, co-registration across runs, normalization to the MNI template, smoothing, motion censoring or “scrubbing” (Power et al. 2012) , physiological artifact correction (Behzadi et al. 2007) , 36-parameter confound regression and spike regression (Satterthwaite et al. 2013)). Regions of interest (ROI) analysis will be performed, with ACC and amygdala as seed regions, to test the hypothesis of decreased BOLD response to negative stimuli and increased BOLD response to positive stimuli in these regions one week and one month post-psilocybin. The first eigenvector of the signal from all voxels in each region will be submitted to a mixed effects repeated measures ANOVA, with time point and the emotional valence of stimuli as within-subject main effects, and subject as a random effect. Subject-level contrasts will assess effects of task condition at each time point. Second-level t-tests will be used for planned comparisons to test the hypothesis of lower BOLD response to negative stimuli and higher BOLD response to positive stimuli post-psilocybin. We will repeat these analyses as whole-brain voxel-wise analyses to evaluate change outside of hypothesized regions. Preprocessing and whole-brain statistical analysis will be conducted using Statistical Parametric Mapping (SPM; <http://www.fil.ion.ucl.ac.uk/spm/software/spm12/>) in MATLAB. ROI analysis will be conducted using MarsBaR (<http://marsbar.sourceforge.net/>).

Secondary Outcome Questionnaire Measures: Repeated-measures ANOVA will be used when appropriate to assess change between groups and over time within groups in secondary outcome measures. Planned

comparisons will investigate change in questionnaire test scores between pre-session and post-session timepoints.

Power Analysis: Assuming a one-way ANOVA with three levels (day before, one week and one month after) and 12 subjects, we have 75.8% power to observe significant connectivity change ($p < 0.05$) for a small observed effect size ($r=0.25$). The proposed study will provide data to directly estimate the effect of psilocybin on longer-term change in emotion and neural circuitry.

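### The plan provides no masking of scan time point for the primary fMRI outcome, although masking is feasible and key processing choices are left open

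*Combined protocol and SAP*

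**What the plan says.** The opening overview describes the design: "This open-label, non-blinded study will involve 12 volunteers who will receive a high dose of psilocybin under supportive conditions". It makes no exception for image processing or outcome analysis. The primary objective is an fMRI measure of emotion circuitry at one week and one month, and scanning "will also be conducted 1 day before, 1 week after, and 1 month after the psilocybin session".

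The only coding described is in the consent and confidentiality text under Inclusion/Exclusion Criteria: "All data will be collected using the unique identification code numbers assigned to each participant upon entry to the study". The same section aims to consent up to 100 people "in order to achieve 12 participants who provide complete data".

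The Statistical plan (neural circuitry paragraph) says that "Whole-brain BOLD EPI data will undergo standard preprocessing". It lists realignment, co-registration, normalisation, smoothing, motion censoring, physiological correction and "36-parameter confound regression and spike regression". ROI analysis follows in two named regions, the amygdala and the ACC. The first eigenvector of each region's signal goes into the ANOVA. The predicted direction after psilocybin is a lower response to negative stimuli and a higher response to positive stimuli.

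The earlier description of the tasks, under Study Statistics, gives the BOLD outcome of the emotion recognition and Stroop tasks as an average response.

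**The concern.** Participants and session staff cannot be blinded in a one-arm open-label study, but the people who process the images can be. In a pre/post comparison, knowing the time point of a scan is the same as knowing whether it is treated. Someone who has that label and the stated hypothesis knows which way each scan is expected to move.

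That matters only if processing leaves something to decide, and here it does. A cited method for censoring or spike regression does not by itself say which threshold is used, when a scan is rejected, or which voxels make up the amygdala. If such decisions are made with the time point known, they can lean toward the expected change without any intent. The result is then hard to tell apart from a drug effect on the primary outcome.

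**Working it through.** The plan gives no figure on this point. Its 75.8% power figure is a separate matter, because masking changes neither the sample size nor alpha. The check is therefore a comparison of the text, followed by two illustrations on assumed inputs.

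**1. What could be masked.** Each of 12 participants has three scans, one before the drug and two after, so 12 × 3 = 36 scans. There is no second arm. Time point is the only treatment label.

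**2. What the text fixes and leaves open.**
- Fixed: the two regions, the software (SPM and MarsBaR), the sequence of steps with methods cited for several of them, and the predicted directions.
- Not stated: the censoring threshold, the smoothing kernel, the rule for rejecting a scan, the ROI mask or atlas, who processes the scans, and whether they know the time point.
- Described in two ways: an average BOLD response (task description, two tasks) and a first eigenvector (Statistical plan). The average may refer to trials rather than voxels, but the text does not say so.
- Consequence of the completeness target: a decision that a scan has failed can change who counts among the 12.

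**3. Illustration A: keeping the best of K pipelines.** Assume no true change, n = 12, and a paired t-test at two-sided 5%, so df = 11 and the critical value is −2.201 in the predicted direction. Under pipeline k, let participant i's change be x_ik = √r·z_i + √(1−r)·e_ik, with independent standard normal z and e, so that pipelines correlate at r. Compute t_k = mean(x_k) / (SD(x_k)/√12) and keep the smallest. The quantity sought is P(min t_k < −2.201), from 60,000 simulated datasets.

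| K | r = 0.9 | r = 0.8 | r = 0.7 |
|---|---|---|---|
| 1 | 2.5% | 2.5% | 2.5% |
| 4 | 4.9% | 5.9% | 7.0% |
| 6 | 5.8% | 7.4% | 8.7% |

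An independent rerun with 200,000 datasets agreed to about 0.1 percentage point. At r = 0.98 and K = 4 the figure is about 3.5%. The plan does not state the sidedness of its planned t-tests. If they are one-sided at 5%, K = 4 gives 9.0–12.5% instead of 5%. All rates are per comparison.

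**4. Illustration B: a small shift in the post-drug scans.** Suppose processing shifts the paired change by d standard deviations of that change. The two-sided rejection rate under no true effect is 1 − F(2.201) + F(−2.201), where F is the noncentral t distribution with 11 df and noncentrality d√12.
- d = 0: 5.0%
- d = 0.1 (noncentrality 0.346): 6.2%
- d = 0.2 (0.693): 9.7%
- d = 0.3 (1.039): 15.8%
- d = 0.5 (1.732): 35.3%

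Neither K and r nor d comes from the documents.

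**The case against.** The strongest reply is that the plan is silent on who handles the scans, and silence is not evidence that labels are visible. The non-blinded statement describes the study as a whole and does not mention image analysts. The participant code is a confidentiality measure, not an account of how scans are labelled. The listed steps are largely algorithmic, and the regions and directions are named in advance. This is also a small, openly declared open-label study meant to estimate an effect.

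Much of this stands, and it rules out several stronger readings that a reader might infer:
- That analysts know which scans are post-drug and steer the result. The documents do not say what the analysts see.
- That manual registration checks or re-registration are a route for bias. The plan describes neither.
- That a control arm would cancel the problem. It would not if the arm label were also visible; cancellation needs masking to arm.
- That the inflation figures size the problem. Illustration A models a choice among whole pipelines on group results, which is broader than scan-by-scan judgement. The direct cure for it is to fix the pipeline, and masking alone is not enough.

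What does not stand is the inference that nothing needs to change. Algorithms still need settings and accept-or-reject rules, and these are not stated. An unqualified non-blinded declaration, with no masking provision anywhere, gives the primary outcome no protection that the plan can point to.

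**Conclusion.** The point holds as a cheap improvement. The plan declares the study non-blinded, provides no masking of scan time point for the primary fMRI outcome, and leaves open the threshold, rejection rule, mask and summary measure that would limit unmasked choices. It does this while stating the expected direction.

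The documents establish opportunity. They do not establish that labels were visible to those processing the scans, that any choice was steered, or how large an effect would be. The range of about 5–7% against 2.5% rests on four pipelines correlated 0.7–0.9 and on selection by group result. It falls to about 3.5% at correlation 0.98 and should be read only as an order of magnitude. The gap does not invalidate the study.

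**What to change.** In the overview and in the neural circuitry paragraph of the Statistical plan, state that the study is open-label for participants and session staff, and that fMRI processing is masked to time point. Then specify the following:

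1. Before preprocessing, a script replaces each participant's three scan labels and dates, including those in image headers and task log files, with random codes. The key is kept away from whoever processes the scans.
2. One pipeline is fixed in advance: the censoring threshold, the scan-exclusion rule, the ROI mask, and a single ROI summary that reconciles the task description with the Statistical plan.
3. Preprocessing, exclusions, subject-level contrasts and ROI values are completed and locked under the codes.
4. Labels are restored only for the group-level ANOVA and planned comparisons. Any later rerun is reported as a sensitivity analysis.

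The cost is a relabelling script, a few sentences in the plan, and someone outside processing to hold the key. No extra scans or participants are needed, and power is unaffected. The one drawback is that scanner checks that depend on dates must be done before masking.

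### Secondary objective 2 covers personality at 1 week and 1 month, but the four personality questionnaires are given only at screening and 1 month, so the 1-week part has no data.

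*Combined protocol and SAP*

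**What the plan says.** The list of secondary objectives includes: "Assess the effects of psilocybin on personality at 1 week and 1 month timepoints after psilocybin administration". Two post-dose times are therefore named for personality.

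The section Longitudinal and Follow-Up Questionnaires lists the Big Five Inventory, the Brief Affective Neuroscience Personality Scales, the Tellegen Absorption Scale and the Emotion Regulation Questionnaire, "which are validated measures of personality traits". Their schedule follows: "These questionnaires will be administered during screening and at the 1-month post-psilocybin imaging session". The stated purpose is "in order to test the hypothesis that openness and positive emotional personality traits will increase, and negative emotional personality traits will decrease" after dosing.

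A separate section, Longitudinal Emotion and Social Questionnaires, has a different schedule: "A battery of questionnaires will be completed one day before, one week after, and one month after psilocybin to assess emotional and social changes". It contains six instruments: the Positive and Negative Affect Scale - X, the Profile of Mood States, the Dispositional Positive Emotions Scale, the Depression Anxiety Stress Scale, the State Trait Anxiety Inventory and the Social Value Orientation test.

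Two analysis statements are relevant. Under Statistical plan: "Outcome measures of the longitudinal questionnaires will be separately submitted to a one-way repeated measures ANOVA, with assessment time-point as a within-subject factor". Under Secondary Outcome Questionnaire Measures, planned "comparisons will investigate change in questionnaire test scores between pre-session and post-session timepoints".

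**The concern.** The objective and the schedule cannot both be carried out. A site following the instrument-level schedule collects no personality scale at 1 week, yet the objective commits the study to an effect at that time.

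This is a gap in data collection. No choice of model can fill it, and once a participant's 1-week visit has passed the measurement is lost. The study is about persisting effects. Without 1-week scores it could not say whether a personality change seen at 1 month was already present at 1 week.

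**Working it through.** The plan gives no figure of its own on this point. The 75.8% in the Power Analysis is stated for connectivity change and does not bear on personality. The check is a cross-reading followed by a count.

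**Inputs**
- Post-dose times in the objective: 2 (Secondary objectives).
- Instruments the plan labels as personality measures: 4 (Longitudinal and Follow-Up Questionnaires).
- Post-dose administrations of those four: 1, at 1 month (same section).
- Participants with complete data: 12 (Inclusion/Exclusion Criteria).

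**Schedule by instrument set**

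| Instrument set | Screening | 1 day before | 1 week | 1 month |
|---|---|---|---|---|
| Four personality scales | yes | no | no | yes |
| Six emotional and social measures | not stated | yes | yes | yes |

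No instrument appears in both rows, so the 1-week battery supplies none of the four personality scales.

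**Count**
- Forms needed to cover both times in the objective with the plan's own scales: 4 instruments × 12 participants × 2 times = 96.
- Forms scheduled: 4 × 12 × 1 = 48.
- Shortfall: 96 − 48 = 48, all at 1 week, which is 48/96 = 50% of the post-dose personality measurements.

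**What can be analysed**
- Each personality scale has two time levels, screening and 1 month. The only available contrast is 1 month minus screening, and the pre-session versus post-session comparison under Secondary Outcome Questionnaire Measures covers it.
- A three-level analysis over baseline, 1 week and 1 month cannot be run on these scales. This matters if the ANOVA under Statistical plan is meant to include them, which is unclear because both questionnaire sections carry the word longitudinal in their titles.

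**The case against.** Five points can be made for the plan.

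1. The opening summary may already cover the visit: "Assessments (questionnaires and emotional tasks) will be conducted during screening sessions, and 1 day before, 1 week after, and 1 month after the high-dose psilocybin". That sentence speaks of questionnaires in general and assigns no instrument to any visit. The sentence scheduling the four scales is specific, and it is the one staff would follow. If the summary did govern, the specific sentence would be wrong and the two would still need reconciling.

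2. The 1-week battery is not free of trait content. By their names, the State Trait Anxiety Inventory and the Dispositional Positive Emotions Scale touch on dispositions, and the personality hypothesis includes emotional traits. But the plan classes both as emotion measures, reserves the personality label for the other four, and describes no instrument in that battery as measuring openness. The lack of 1-week data therefore holds for personality as the plan itself defines it.

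3. The objective names no instruments, so 96 forms is not its literal requirement; one personality scale at 1 week would give it some data. That is fair. The count expresses, using the plan's own scales, that one of two promised times is unscheduled.

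4. The time phrase may have been carried over from secondary objective 1, and leaving traits out at 1 week may be deliberate. Either is possible. The document gives no such reason, and in either case the objective's wording has to change.

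5. The extracted text mentions numbered visits but contains no full visit table, so the conclusion applies to the text as available.

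What stands is that the consequence is limited: this is a secondary objective in a small open-label study, and the hypothesis attached to the four scales does not itself name 1 week.

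**Conclusion.** The concern holds. The objective and the instrument schedule contradict each other. As written, one of the two times in secondary objective 2 has no personality data: 0 of 48 forms at 1 week if all four scales are counted for 12 participants. The conclusion rests on two readings: that the specific schedule takes precedence over the general summary, and that personality means the four instruments the plan gives that label.

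The primary objective, secondary objective 1 and the screening-to-1-month personality comparison are unaffected. This should be corrected, but it does not threaten the main result.

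**What to change.** Either of two changes resolves it.

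- **Add the measurement.** Amend Longitudinal and Follow-Up Questionnaires so that the four scales are given at screening, 1 week and 1 month. The pre-session versus post-session comparison then covers both post-dose times with no new analysis. The cost is extra self-report time at a visit participants already attend for fMRI and six questionnaires: 6 + 4 = 10 instruments, with no new visit.
- **Narrow the objective.** Remove 1 week from secondary objective 2, so that it concerns the change from screening to 1 month. The cost is a wording change and giving up the 1-week personality question.

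Adding the measurement keeps the objective as stated. If 1-week trait data were never wanted, narrowing the objective is enough. In both cases the Statistical plan should say which analysis applies to the four scales and that their baseline is screening, not the day before dosing.
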